## C. Sample Size, Statistical Methods, and Power Calculation

### C1. Analytic and statistical methods (including randomization)

**Randomization.** Thirty-six primary care practices from the rural Midwestern U.S. will be randomly allocated in equal proportions (1:1:1) to each of the three arms (FFS, PCMH, DM). Randomization will be stratified by institutional affiliation (KUMC, UNMC, Marshfield Clinic) within three cohorts.

**Missing data.** Based on our prior history using a similar retention plan in the rural setting, we expect to retain a minimum of 80% of participants (with a goal of 90%) at 24 months across all three treatment arms. We will document reasons for loss to follow-up. Participants who are removed from study for pregnancy, bariatric surgery, medical safety reasons, behavioral problems, or death will be excluded from analyses. All primary analyses will be conducted using intent-to-treat. We will evaluate the missing data pattern for differential loss to follow-up based upon treatment arm. All of the covariates (other than the outcomes) will be collected at baseline, and with our data quality controls we don't expect this data to be missing. In the absence of differential loss to follow-up, missing weight data will be treated as missing at random and addressed using maximum likelihood methods.

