### **Secondary aim 6: evaluate the reach and sustainability of the interventions with the RE-AIM framework (Reach, Adoption, Implementation, Maintenance)**

Adoption within KUMC-affiliated sites will be evaluated by comparing practice characteristics across participating and non-participating practices (that were contacted about the study) using two sample comparisons (chi square or t-tests). After aggregating to the practice level, patient-level factors for reach (e.g., participation rates) and implementation (e.g., session attendance, ratings of care) will be tested and compared across arms using separate analysis of variance (ANOVA) models. Maintenance of weight loss services at the practice-level will be reported as simple frequencies.

**Potential confounders:** For all statistical models, sensitivity analyses will be performed using the models above but also adjusting for potential confounders among the baseline variables identified as varying across arms based on their standardized differences.

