### **C3. Power calculation and sample size**

A total of 36 practices with 40 participants per practice will be enrolled in the study (1440 participants total). Twelve practices (480 participants total) will be enrolled in each arm (FFS, PCMH, DM). A net treatment effect of 2.75 kg is supported by the available literature and our previous work. Treatment effects for PCP counseling alone with varying levels of intervention intensity have ranged from 0.1 to 1.7 kg at 12 to 24 months follow-up with the majority falling below 1 kg. For this pragmatic trial conducted in underserved rural areas, we expect the FFS treatment effect to fall in the lower end of this range. Team-based care approaches with obesity counseling delivered by auxiliary staff (PCMH) have ranged from 2.9 to 5.1 kg at 24 mo. In an entirely remote disease management program, Appel et al. reported weight loss of 4.6 kg at 24 mo. Our remote group phone-based program currently being delivered outside the primary care setting has shown 10.2 kg loss at 18 mo in preliminary analyses. We expect this to be lower in a pragmatic primary care trial, however a net effect  $\geq 2.75$  kg is achievable. To determine sample size, we set the type I error at 0.025 (overall type I error rate of 0.05 for first two aims), intraclass correlation coefficient at 0.05, and 40 patients/clinic. With 36 clinics, the trial will have 80% power to detect a net treatment effect of 2.75 kg (SD = 8).

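### The adjusted sensitivity analyses select covariates by observed imbalance between arms, with no cutoff, three-arm rule or candidate list, so chance and a later choice settle the adjustment set

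*Combined protocol and SAP*

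**What the plan says.** The rule is in section II.C1, in the paragraph on potential confounders that closes the statistical methods. It is printed under Secondary aim 6 but covers the whole plan: "For all statistical models, sensitivity analyses will be performed using the models above", this time "adjusting for potential confounders among the baseline variables identified as varying across arms based on their standardized differences".

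Nothing else in II.C1 narrows this. The missing-data paragraph says that "All of the covariates (other than the outcomes) will be collected at baseline" and expects none to be missing, but names none. The text on aims 1 to 3 describes hierarchical mixed models with clinic and patient correlation and lists no adjustment covariates. It also allows the analytical plans to be adapted.

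**The concern.** A standardized difference estimated from 12 practices per arm is a noisy statistic, and the plan lets it decide which covariates enter. Three things follow.

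- Variables with no systematic difference can enter by chance, while variables with a real small difference can stay out.
- A strong predictor of weight change that happens to look balanced is left out, although including it would add precision.
- Because the cutoff and the handling of three arms are not written down, the set cannot be known until baseline data by arm have been examined, in a trial where staff are not blinded (II.C2).

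Adjustment matters more here than in an individually randomized trial. Practices are allocated first. The consent form differs by arm (II.I, IRB-approved protocols), patients unable to attend their arm's type of visit are recorded as declining (II.D1), and enrolment runs 9 months in FFS against 6 months in the other arms (II.E5). Systematic differences in who enrols are possible. If the adjusted result differs from the unadjusted one, or agrees with it, a reader needs to know that the covariate set did not depend on an unwritten choice.

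**Working it through.** **Inputs from the plan (II.C3).** 12 practices of 40 patients, so 480 per arm; "intraclass correlation coefficient at 0.05" for the outcome; SD 8 kg; target difference 2.75 kg; type I error 0.025 per comparison; power 80%.

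**Assumptions, because the plan is silent.** Covariate ICC 0.01 to 0.05; cutoff 0.10 or 0.20; a variable is flagged if any of the three arm pairs exceeds the cutoff; correlation between covariate and weight change 0.3. Standardized differences are treated as normal, clusters as equal, and any gain from stratification is ignored.

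**1. The plan's own figure.** Design effect = 1 + 39 × 0.05 = 2.95. Effective n = 480 / 2.95 = 162.7 per arm. SE = 8 × √(2 / 162.7) = 0.887 kg. Two-sided alpha 0.025 gives power 80.5%, so the stated 80% reproduces. No covariate enters this calculation.

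**2. Noise in a standardized difference.** SE = √(2 × DE / 480), with DE = 1 + 39 × ICC.
- ICC 0.01: DE = 1.39, SE = 0.076.
- ICC 0.05: DE = 2.95, SE = 0.111.

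**3. How often the rule flags or misses a variable.** Three arm means were simulated with variance DE / 480 each. For the misses, one arm was shifted by 0.10.

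| Covariate ICC | No true difference, flagged at 0.10 | Same, at 0.20 | True 0.10, unflagged at 0.10 | Same, at 0.20 |
|---|---|---|---|---|
| 0.01 | 38.8% | 2.3% | 29.9% | 83.7% |
| 0.05 | 63.9% | 16.8% | 23.5% | 67.6% |

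For an illustrative 15 candidates with no true difference, that is 15 × 0.388 = 5.8 to 15 × 0.639 = 9.6 chance flags at cutoff 0.10, and 15 × 0.023 = 0.3 to 15 × 0.168 = 2.5 at cutoff 0.20. The current text permits either cutoff.

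**4. What a missed covariate costs.** An omitted covariate shifts the estimate by realised imbalance × correlation × SD = imbalance × 0.3 × 8 = imbalance × 2.4 kg. When a covariate is missed, its realised imbalance is at most the cutoff. For one pair with true difference 0.10 and cutoff t, the mean realised imbalance among missed trials is 0.10 + SE × [φ(a) − φ(b)] / [Φ(b) − Φ(a)], where a = (−t − 0.10) / SE and b = (t − 0.10) / SE.
- Cutoff 0.10: 0.041 (ICC 0.01) and 0.023 (ICC 0.05), which is 0.10 and 0.06 kg. The ceiling is 0.10 × 2.4 = 0.24 kg.
- Cutoff 0.20: 0.086 and 0.065, which is 0.21 and 0.16 kg. The ceiling is 0.20 × 2.4 = 0.48 kg.

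At cutoff 0.10 the average shift is 0.06 / 2.75 = 2% to 0.10 / 2.75 = 4% of the target difference. The ceiling is 0.24 / 2.75 = 9% of it, or 0.24 / 0.887 = 27% of one SE.

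**5. Precision forgone.** A covariate with correlation 0.3 explains 0.3² = 9% of outcome variance, whether or not it is balanced. Selection by imbalance gives up that gain when the variable looks balanced.

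**The case against.** The strongest reply is that this is a sensitivity analysis driven by baseline variables, not outcomes, and that checking observed imbalance is sensible when patients are recruited after their practice is allocated. Much of that stands. An imbalance in a prognostic variable shifts the estimate whether it arose by chance or by selection, so entering a chance-imbalanced variable is not an error in itself. The imbalance check is worth keeping.

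A reader might also infer stronger faults that the documents do not support.

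- *The rule ignores prognosis.* The text restricts selection to potential confounders, which ordinarily implies a relation to outcome. The weakness is that the term is not defined.
- *The rule misses about half of real small imbalances.* That follows almost automatically if the true difference is set equal to the cutoff and only one pair is examined (46% to 50% at 0.10). On the any-pair rule it is 30% to 24%, and no document fixes either number.
- *Most variables entered are chance findings.* At a pairwise cutoff of 0.10, with real differences of 0.10, the chance share runs from 20% to 86%. It depends on the unknown fraction of candidates that truly differ and on unknown covariate ICCs (0 to 0.05 here).
- *Each missed covariate costs 0.24 kg.* That is the ceiling at cutoff 0.10, not the expected shift.
- *This is the plan's only protection against confounding.* Randomization is stratified by institution within cohorts (II.C1), recruitment is mainly by mailing to practice registries (III.A), and telephone screening is centralised (III.B). It is, however, the only covariate adjustment that the analysis plan describes.

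What the reply does not answer is that cutoffs of 0.10 and 0.20 yield very different adjustment sets and the plan chooses neither.

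**Conclusion.** The concern holds as a weakness in how the adjusted sensitivity analyses are specified. Their covariate set rests on noisy observed imbalance and on a cutoff and three-arm rule still to be chosen, and prognostic variables that look balanced are dropped. Moving the cutoff from 0.10 to 0.20 changes the chance-flag rate from 39%–64% to 2%–17%, and the rate of missing a true 0.10 difference from 24%–30% to 68%–84%.

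The consequence for the weight estimate is modest: about 0.06 to 0.10 kg on average for one missed covariate at cutoff 0.10, although several omissions in the same direction would add up. All these figures rest on the assumed covariate ICC, cutoffs and correlation listed above. The primary models and the power statement do not depend on the rule. The main loss is in how far a reader can rely on agreement between adjusted and unadjusted results.

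**What to change.** In the potential-confounders paragraph of II.C1, make the main adjusted sensitivity analysis use one fixed list of baseline prognostic variables, whatever their balance. Suitable variables that are already collected, or can be derived from what is collected (II.E2e), include baseline weight, age, race/ethnicity, education, income, employment, home-to-clinic distance, weight-loss history and smoking. Several of these are already named in Secondary aim 5 as likely to affect response. Sex is another natural candidate, but the demographic list in II.E2e does not name it, so its capture should be confirmed first. The practice-level ANOVA models of Secondary aim 6 have only 36 units and would need a shorter, practice-level list.

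Keep the standardized-difference rule as an additional analysis, with the cutoff stated and a sentence on how three arms are combined (any pair, or each contrast separately). This still catches an imbalanced variable that is not on the fixed list.

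The cost is a few sentences in the plan, one further sensitivity model per outcome and a few more parameters. No new data collection is needed for the variables listed, and the plan does not expect baseline covariates to be missing.

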## **C2. Blinding**

Randomization happens at the practice level. Blinding practice staff or study staff is not feasible during a behavioral trial. However, throughout the study investigators and study personnel will communicate and

demonstrate equipoise (genuine uncertainty) with practice staff and patients about the relative benefit of the three arms.

### **C3. Power calculation and sample size**

A total of 36 practices with 40 participants per practice will be enrolled in the study (1440 participants total). Twelve practices (480 participants total) will be enrolled in each arm (FFS, PCMH, DM). A net treatment effect of 2.75 kg is supported by the available literature and our previous work. Treatment effects for PCP counseling alone with varying levels of intervention intensity have ranged from 0.1 to 1.7 kg at 12 to 24 months follow-up with the majority falling below 1 kg. For this pragmatic trial conducted in underserved rural areas, we expect the FFS treatment effect to fall in the lower end of this range. Team-based care approaches with obesity counseling delivered by auxiliary staff (PCMH) have ranged from 2.9 to 5.1 kg at 24 mo. In an entirely remote disease management program, Appel et al. reported weight loss of 4.6 kg at 24 mo. Our remote group phone-based program currently being delivered outside the primary care setting has shown 10.2 kg loss at 18 mo in preliminary analyses. We expect this to be lower in a pragmatic primary care trial, however a net effect  $\geq 2.75$  kg is achievable. To determine sample size, we set the type I error at 0.025 (overall type I error rate of 0.05 for first two aims), intraclass correlation coefficient at 0.05, and 40 patients/clinic. With 36 clinics, the trial will have 80% power to detect a net treatment effect of 2.75 kg (SD = 8).

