#### A2. Aims and hypotheses

##### *Primary Aims:*

1. Test the hypothesis that **PCMH (in clinic group visits)** is more effective than **FFS (in clinic individual visits)** in reducing weight at 24 months.
2. Test the hypothesis that **DM (phone group visits)** is more effective than **FFS (in clinic individual visits)** in reducing weight at 24 months.

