### **Primary aims 1-3: weight loss at 24 months and leading up to 24 months**

Weight loss at 24 months will be compared between PCMH vs FFS and DM vs FFS, as well as DM vs PCMH. Hierarchical linear mixed models will be used to examine the group differences, accounting for the correlation between patients from the same clinic.

We will fit a hierarchical linear mixed model with longitudinal weight change at 6, 18, and 24 months study visits. This model will account for the correlation between patients in the same clinic as well as correlation of measures from the same patient. In secondary analysis, percent weight loss will also be compared across the three groups using the same approach. Clinical cutpoints of 5% and 10% will be compared across arms at 6 and 24 months using generalized linear mixed models. The analytical plans may be adapted to provide the best approach using the latest methodological advancements.

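### Naming Holm for the two primary comparisons would keep the overall 0.05 and add power at no cost; the apparent 0.025/0.025 split is valid but less efficient

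*Combined protocol and SAP*

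**What the plan says.** Section I.A2 lists two separate primary aims: PCMH against FFS and DM against FFS, both on weight at 24 months. DM against PCMH is listed there as secondary.

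Multiplicity is addressed once, in section II.C3, as part of setting the sample size: "we set the type I error at 0.025 (overall type I error rate of 0.05 for first two aims". The same section gives the other design inputs and concludes that "the trial will have 80% power to detect a net treatment effect of 2.75 kg (SD = 8", with the "intraclass correlation coefficient at 0.05" and 12 practices of 40 patients per arm.

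The primary analysis text in II.C1 states which contrasts are made: "Weight loss at 24 months will be compared between PCMH vs FFS and DM vs FFS, as well as DM vs PCMH". It names a hierarchical linear mixed model but no test level and no rule for combining the primary tests. It also allows the analysis plan to be adapted to newer methods. No step-wise, Dunnett-type or fixed-sequence procedure appears anywhere. Section V.A rules out interim analyses, so no alpha is spent on interim looks.

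**The concern.** If each primary test is judged at 0.025 whatever the other shows, the plan uses the least powerful common way of holding 0.05 over two tests. Once one null hypothesis has been rejected at 0.025, the other can be tested at the full 0.05 with the family error still at or below 0.05.

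The results at stake are those where one arm clearly beats FFS and the other has a two-sided p-value between 0.025 and 0.05. Under the split, the second model of care is not declared better than FFS. Under Holm, the same data at the same family error support the claim. Sections II.A and V.B describe the aim and expectation as both alternative models outperforming FFS, so this affects a conclusion the trial wants to draw.

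**Working it through.** **Inputs.** From II.C3: effect 2.75 kg, SD 8, ICC 0.05, 12 practices per arm, 40 patients per practice, 0.025 per test. From II.C1: 1:1:1 allocation and at least 80% retention (32 per practice). Assumed: two-sided tests (sidedness is not stated; see step 1) and, for the t version, 36 − 3 = 33 degrees of freedom.

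**1. Reproduce the stated 80%.**
- Design effect = 1 + 39 × 0.05 = 2.95.
- SE of a difference = √(2 × 64 × 2.95 / 480) = 0.887 kg, so effect/SE = 2.75 / 0.887 = 3.10.
- Power at two-sided 0.025 (critical value 2.241) = Φ(3.10 − 2.241) = 80.5%, which matches.
- One-sided 0.025 (critical value 1.960) would give 87.3%, which does not match. Two-sided testing is therefore inferred.

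**2. Correlation of the two tests.** Both contrasts subtract the same FFS mean. With equal arms, their covariance is half the variance of each difference, so the correlation is 0.5.

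**3. The two rules.**
- Split: reject each null if |z| > 2.241.
- Holm: compare the larger |z| with 2.241. If it passes, compare the other with 1.960.

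Holm adds a rejection only when one statistic exceeds 2.241 and the other lies between 1.960 and 2.241. It never removes one.

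**4. Power with both true effects at 2.75 kg** (simulation, 2 to 4 million draws; gains taken before rounding). With 32 per practice, the design effect is 1 + 31 × 0.05 = 2.55 and SE = √(2 × 64 × 2.55 / 384) = 0.922 kg.

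| Per practice, reference | Per aim: split → Holm | Gain (points) | Both aims: split → Holm | Gain (points) |
|---|---|---|---|---|
| 40, normal | 80.5% → 85.0% | 4.5 | 69.4% → 78.4% | 9.0 |
| 40, t (33 df) | 77.0% → 82.1% | 5.1 | 65.2% → 75.3% | 10.1 |
| 32, normal | 77.1% → 81.9% | 4.8 | 64.8% → 74.4% | 9.7 |
| 32, t (33 df) | 73.5% → 78.8% | 5.3 | 60.6% → 71.2% | 10.7 |

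Power for at least one success is the same under both rules: 91.6% in the first row and 88.8% in the second.

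**5. Other true effects** (40 per practice, normal).

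| True effects (kg) | Gain per aim (points) | Gain for both (points) |
|---|---|---|
| 2.0 and 2.0 | 5.2 | 10.4 |
| 3.5 and 3.5 | 1.7 | 3.4 |
| 4.0 and 4.0 | 0.6 | 1.1 |
| 2.75 and 2.0 | weaker arm 9.1 (50.5% → 59.6%) | 11.0 |
| 2.75 and 0 | effective arm about 0.15 | not applicable |

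**6. Error rates.** With both nulls true, the chance of any false claim is 4.65% (normal) or 4.63% (t) under either rule. With one arm effective at 2.75 kg and the other null, the null arm's false-positive rate is 2.5% under the split and 4.2% to 4.3% under Holm, still below 5%.

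**The case against.** The best reply is that nothing here is wrong. An equal split is a standard, valid way to hold 0.05, and the chance of at least one positive primary result is the same under both rules. This stands and determines how the point is classed.

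A reader might infer that the protocol has fixed 0.025 as the decision threshold. The documents do not go that far: II.C3 introduces the figure as a sample-size input, and II.C1 is silent on the rule. Sizing at 0.025 is also what one would do before analysing by Holm. The split is the natural reading because no other rule is given, but it remains an inference.

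A reader might also infer that the split gives up power for no protection at all. That is too strong. The split comes with 97.5% intervals that agree with every decision, and it holds an ineffective arm's false-positive rate at 2.5% even when the other arm works. These are real, if modest, benefits. They lie beyond the family error rate, which is the only target II.C3 sets.

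Finally, the gain is conditional. II.C3 regards a net effect of at least 2.75 kg as achievable. It cites 2.9 to 5.1 kg for team-based care and 4.6 kg for a remote programme, with most PCP-counselling effects below 1 kg. At larger net effects the gain is small, as step 5 shows. II.C3 also does not set joint power for both aims as its target. Against that, 2.75 kg is the plan's own design value, and the gain stays large at 2.0 kg.

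**Conclusion.** The point holds as a cheap improvement, not as an error. On the natural reading of II.C3, and with both true effects at the planned 2.75 kg, Holm would add 4.5 to 5.3 points of power per aim and 9.0 to 10.7 points for showing both, with family error still at or below 0.05. The lower ends come from full data with normal quantiles. The upper ends come from 80% retention with a t reference.

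These figures rest on two-sided tests, a correlation of 0.5 from the shared FFS arm, and the SD and ICC in II.C3. They do not support an unconditional claim of lost power. The gain falls to about 1.7 and 3.4 points if both effects are 3.5 kg, is about 0.15 points for the effective arm if the other does nothing, and is zero for at least one success. The sample size is unaffected, because Holm's first step is also taken at 0.025.

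**What to change.** Add to II.C1, before outcome data by arm are seen:

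> *Aims 1 and 2 are tested by the Holm procedure at overall two-sided 0.05: the smaller p-value against 0.025 and, if significant, the larger against 0.05.*

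Keep 0.025 in II.C3 as the sample-size basis. The timing matters because II.C1 leaves the analysis open to adaptation, and a rule chosen after seeing results by arm would not be credible. The sentence also fills the gap in II.C1, where no decision rule is stated. It makes explicit that the family is Aims 1 and 2, although the II.C1 heading groups aims 1 to 3 as primary.

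The cost is one sentence, with no change to patients, data or sample size. The plan should acknowledge two downsides. If 97.5% intervals are reported, an arm with p between 0.025 and 0.05 can be declared superior under Holm while its interval includes zero. An ineffective arm's false-positive rate can also rise from 2.5% to about 4.3% when the other arm works, with family error still at or below 5%.

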# **II. RESEARCH PLAN AND DESIGN**

## **A. Study Objectives**

**Research Goal:** To advance our knowledge of obesity treatment in rural primary care by directly comparing the effectiveness of two alternative models of care with the current standard of care. If the hypotheses are correct, the results may warrant a new standard of care for obesity treatment in rural primary care practices.

**Study Aims:** The primary aims of the study are to test the hypotheses that both the PCMH model (with in clinic group visits) and DM model (with group phone visits) are more effective than the currently reimbursed FFS model (with in clinic individual visits) in reducing weight at 24 months.

[figure not shown]
The secondary aims of the study are to 1) test the hypothesis that the DM is more effective than the PCMH model in reducing weight at 24 months, 2) to compare the effects of the three arms on patient-centered outcomes (i.e. blood pressure, fasting glucose and lipids, quality of life, sleep, and stress), 3) to assess the heterogeneity of treatment effects across demographic subgroups (i.e. race/ethnicity, education level, income level, employment status, and distance traveled/travel time to receive care), and 4) to evaluate the reach and sustainability of the three arms following the RE-AIM evaluation framework.

**Statement of Purpose:** The purpose of this study is to test the comparative effectiveness of three viable treatment models for addressing obesity in rural primary care.

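### The 80% power in II.C3 assumes that all 40 enrolled patients per practice are analysed; at the 80% completeness the plan accepts it is about 77% by normal approximation

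*Combined protocol and SAP*

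**What the plan says.** II.C3 fixes the enrolment target: "A total of 36 practices with 40 participants per practice will be enrolled in the study (1440 participants total"), with 12 practices and 480 participants per arm. The same section uses 40 patients per clinic as the cluster size in the power calculation, with an ICC of 0.05. On error it says "we set the type I error at 0.025 (overall type I error rate of 0.05 for first two aims"). It then concludes: "With 36 clinics, the trial will have 80% power to detect a net treatment effect of 2.75 kg (SD = 8"). It does not mention loss to follow-up, variation in practice size or a reference distribution. It does not say whether 0.025 is one- or two-sided; the aims in II.A are directional (PCMH and DM "are more effective than the currently reimbursed FFS model").

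On completeness, II.C1 says "we expect to retain a minimum of 80% of participants (with a goal of 90%) at 24 months across all three treatment arms". V.B lists, as conditions for adequate power, an average of 40 enrolled per practice and at least 80% complete 24-month weights.

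On analysis, II.C1 says: "Hierarchical linear mixed models will be used to examine the group differences, accounting for the correlation between patients from the same clinic". In the absence of differential loss, "missing weight data will be treated as missing at random and addressed using maximum likelihood methods". II.E2e and III.C4 allow missing weights to be taken from chart review. II.C1 also states: "Participants who are removed from study for pregnancy, bariatric surgery, medical safety reasons, behavioral problems, or death will be excluded from analyses".

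**The concern.** The number enrolled and the number that enters the power formula are the same 40 per practice. A plan that expects to lose up to a fifth of its 24-month weights would normally enrol more than it needs, or quote power at the reduced number. This plan does neither, so its headline power belongs to a completeness it does not require of itself.

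At stake is the benchmark for the two primary contrasts. If one is non-significant, readers will take 2.75 kg as the difference the trial had an 80% chance of detecting. At the accepted completeness that difference is somewhat larger. Because the tested units are 36 practices, the choice between normal and small-sample critical values also matters, and the plan leaves it open.

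**Working it through.** **Inputs.** From II.C3: difference 2.75 kg, SD 8, ICC 0.05, 12 practices per arm, 40 per practice, type I error 0.025 per contrast. From II.C1 and V.B: 80% minimum completeness, with a 90% goal in II.C1. My assumptions: 0.025 is two-sided; practices are equal in size; for the t figures, df = 36 practices − 3 arms = 33.

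**Formulas.** With m analysed per practice:
- Design effect DE = 1 + (m − 1) × 0.05.
- SE of an arm difference = 8 × √(2 × DE / (12m)).
- Normal power = Φ(2.75/SE − 2.2414).
- t power: noncentral t on 33 df, noncentrality 2.75/SE, critical value 2.3483.

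**Reproducing the plan's figure.** At m = 40, DE = 1 + 39 × 0.05 = 2.95 and SE = 8 × √(5.90/480) = 0.887. Then 2.75/0.887 = 3.10, and Φ(3.10 − 2.24) = 80.5%. One-sided 0.025 (critical value 1.96) would give 87.3%. The stated 80% therefore matches two-sided 0.025, a normal reference and all 40 analysed.

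**Allowing for loss (completers only).** At m = 32, DE = 1 + 31 × 0.05 = 2.55 and SE = 8 × √(5.10/384) = 0.922. Then 2.75/0.922 = 2.98, and Φ(2.98 − 2.24) = 77.1%.

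| Analysed per practice | DE | SE (kg) | Power, normal | Power, t 33 df | Detectable at 80%, normal | Detectable at 80%, t 33 df |
|---|---|---|---|---|---|---|
| 40 (none lost) | 2.95 | 0.887 | 80.5% | 77.0% | 2.73 kg | 2.84 kg |
| 36 (90% goal) | 2.75 | 0.903 | 79.0% | 75.4% | 2.78 kg | 2.89 kg |
| 32 (80% minimum) | 2.55 | 0.922 | 77.1% | 73.5% | 2.84 kg | 2.96 kg |

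**Separating the two causes.** Loss costs 80.5 − 77.1 = 3.4 points on the normal scale and 77.0 − 73.5 = 3.5 points on the t scale. Moving from normal to 33 df costs 80.5 − 77.0 = 3.5 points with no loss at all.

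**Sensitivity at m = 32 (normal / 33 df).**
- Unequal practices, assumed CV of size 0.2 to 0.4, with DE = 1 + ((CV² + 1)m − 1) × 0.05: 75.9 to 72.6% / 72.3 to 68.9%. If the mixed model weights practices by precision, the drop is smaller: 76.7 to 75.3% / 73.0 to 71.7%.
- ICC 0.04 to 0.06 instead of 0.05: 82.7 to 71.7% / 79.4 to 68.0%.

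**Ceiling if missing weights are recovered.** Participants excluded under II.C1 cannot be recovered. If an assumed 2 to 5% are excluded and every other weight is obtained (m = 39.2 to 38), power is 80.2 to 79.8% / 76.7 to 76.3%.

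**The case against.** **Completers-only is not the planned analysis.** The model uses 6-, 18- and 24-month weights with maximum likelihood, chart-review weights may fill gaps, and rescheduled 24-month visits have a 4-month window. Eighty per cent is a minimum, and II.I3 reports 85–90% retention in the site investigators' trials. Suppose 80% are complete, half of the 8 missing per practice have an 18-month weight, and its correlation with the 24-month value is 0.7 to 0.9 (all assumed beyond the 80%). A rough gain is 4 × 0.49 to 4 × 0.81, or 2.0 to 3.2 patients per practice, and normal power is about 78.0 to 78.6%. This stands: 77.1% is a floor for loss to follow-up, and the likely shortfall is smaller. It does not cover the exclusions in II.C1, and the plan does not say whether these count within the 80%.

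**Sidedness.** With one-sided 0.025, power at 32 would be 84.7% (normal) or 82.5% (33 df) and the shortfall would vanish. But that reading gives 87.3% at C3's own inputs, so it does not explain the stated 80%. The conclusion is conditional on the two-sided reading, which is the better supported one.

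**Stronger readings that the documents do not support.**
- A reader might infer that attrition takes power from 80% to 73.5%. It does not: about half of that gap is the 33 df reference, which is my choice and applies with complete data.
- A reader might infer that C3 is miscalculated. Its arithmetic is right at its inputs; what is missing is an allowance.
- A reader might infer that V.B contradicts C3. V.B speaks of adequate power and gives no percentage, and 77% is not plainly inadequate.
- A reader might infer that the primary tests will be anti-conservative. Normal critical values on 33 df would give an error of about 0.032 per contrast, but nothing in the plan says they will be used.

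**Conclusion.** The point holds as a minor correction to the power statement. C3's 80% is delivered only with all 40 enrolled patients per practice analysed. At the completeness the plan accepts, loss alone lowers it to no less than about 77% (79% at the 90% goal) by normal approximation, and the difference detectable with 80% power moves from 2.73 to 2.84 kg, just above the planned 2.75 kg. This rests on two-sided 0.025, equal practices, ICC 0.05, SD 8 and any exclusions being counted within the 80%.

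Separately from loss, a between-practice reference gives 77.0% at 40 and 73.5% at 32, and unequal practice sizes would lower either figure further. The loss effect is smaller than that of an error of 0.01 in the planning ICC, so nothing here calls the design or the sample size into question.

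**What to change.** Restate the last sentence of II.C3 along these lines: *two-sided 0.025 per contrast; power for 2.75 kg (SD 8, ICC 0.05) is about 77–80% by normal approximation, or 73–77% with between-practice df, for 80–100% complete 24-month weights and equal practice sizes.* Add that the upper ends require that no participant is excluded from analysis, and say whether the exclusions in II.C1 count towards the 80%. Cross-refer to this statement from V.B, so that its reference to adequate power has a figure behind it. In II.C1, name a small-sample df method for the primary mixed model (Kenward-Roger or between-practice df).

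The cost is a slightly less favourable power statement and a few sentences, fixed before the 24-month comparison is run. Enrolment, data collection and conduct do not change, and there is no case for enrolling more. Holm over the two primary contrasts would be an optional gain in power; it is not part of this correction, since the 0.025/0.025 split is valid.
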